Study Duration	Participants will be scheduled to participate in the study for 12 months or 52 weeks. Accrual will require approximately 4 months (16 weeks).
Duration of participation	Each participant will be scheduled to receive study product for 52 weeks.
Primary endpoints	
Acceptability
 
 ○ The proportion of participants who report willingness to use the study regimen, take up PrEP and remain on PrEP as part of a comprehensive prevention package. ○ Assessment of acceptability as per questionnaire administered at study end. 
Use
 
 ○ Number of adolescents who continue to use PrEP after the initial 3 month period. ○ The total time on PrEP for each adolescent and for the cohort as a whole by self report. 
Safety
 
 ○ Grades 2, 3, and 4 clinical and laboratory adverse events;

Secondary endpoints	
Adherence:
 
Adherence to daily regimens of oral PrEP as evidenced by the use of self-report, pill counts, and proportion of participants on FTC/TDF who have detectable drug levels, in those participants who have indicated willingness to take PrEP and who have had tablets administered
 
 ○ Proportion of doses that are taken as instructed. ○ Proportion of blood samples with detectable drug levels ○ Proportion of adolescents with detectable drug levels who report using PrEP ○ Proportion of scheduled HIV testing appointments missed, in relation to individual characteristics (age, sex, number of partners, use of other prevention methods) and the characteristics of the product. 
Sexual Behavior
 
 ○ Reported number of steady and casual sex partners, condom use (and change after introduction of study product), substance use prior to or during sex, as evidenced by participant responses to interviewer-administered questionnaires and focus groups. 
HIV Incidence
 
HIV infection, as measured by seroconversion of study participants during the approximate 12 months (52 weeks) of follow-up.

---------------------	--

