4.2 SUMMARY OF MAJOR ENDPOINTS

Primary endpoints:

Acceptability

- The proportion of participants who report willingness to use the study regimen, take up PrEP and remain on PrEP as part of a comprehensive prevention package.

- Assessment of acceptability as per questionnaire administered at study end.

Use

- Number of adolescents who continue to use PrEP (as indicated by DBS/ plasma levels) after the initial 3 month period
- The total time on PrEP for each adolescent (as indicated by DBS/plasma levels) and for the cohort as a whole in those individuals who indicated PrEP use by self report at the beginning of each 3 month period.

Safety

- Grades 2, 3, and 4 clinical and laboratory adverse events;

Secondary endpoints:

Adherence:

- Adherence to daily regimens of oral PrEP as evidenced by the use self-report, pill counts, and proportion of participants on FTC/TDF who have detectable drug levels. Proportion of blood samples with detectable drug levels
- Proportion of adolescents with detectable drug levels who report using PrEP
- Proportion of doses that are taken as instructed.

Sexual and other Behaviors

- Reported number of steady and casual sex partners, condom use (and change after introduction of study product), substance use prior to or during sex, as evidenced by participant responses to interviewer-administered questionnaires and focus groups.
- Proportion of scheduled HIV testing appointments missed, in relation to individual characteristics (age, sex, number of partners, use of other prevention methods) and the characteristics of the product.

HIV infection,

- as measured by seroconversion of study participants during the approximate 12 months of follow-up.

Exploratory endpoints:

Impact on adherence of providing information on drug (FTC/TDF) levels (as measured in Dried Blood Spot/Plasma) given as feedback during counseling sessions.

- Number of counselling opportunities in which drug level feedback is requested vs total number of counseling events
- Number and nature of participants who request drug level feedback.
- Correlation between self reported adherence and drug levels at each visit for each participant
- Correlation between self reported adherence and drug levels at each visit in the study overall.
- Proportion and number of participants whose adherence to study product improves when receiving the results of DBS/Plasma compared to those who do not receive feedback of results as measured by endpoints above.

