10.2 STUDY ENDPOINTS

Primary Acceptability/Use Endpoints:

Consistent with the primary study objective to evaluate the acceptability and use of daily oral PrEP (FTC/TDF) in HIV-negative adolescents, ages 15-19 years, the following primary safety endpoints will be assessed:

- The proportion of participants who report willingness to use the study regimen, take up PrEP and remain on PrEP as part of a comprehensive prevention package.
- An acceptability questionnaire will be administered at the final study visit to assess the delivery of PrEP and the content of the study visits, including the user-friendliness of the medication regimen (including an assessment of side effects), the delivery format, the dosing strategy, and the clinic visit schedule.
- Number of adolescents recruited, enrolled, and retained in the study.

Primary Safety Endpoint:

- Grades 2, 3, and 4 clinical and laboratory adverse events;

Secondary Endpoints:

Consistent with the secondary study objectives to evaluate the adherence and sexual behaviour of daily oral PrEP (FTC/TDF) in HIV-negative adolescents, ages 15-19 years, the following endpoint will be assessed:

Adherence Endpoint:

- Adherence to daily regimens of oral PrEP as evidenced by self-report, pill counts, and proportion of participants assigned to FTC/TDF who have detectable drug levels.
 - Proportion of doses that are taken as instructed.

Sexual behaviour

- Reported number of steady and casual sex partners, condom use (and change after introduction of study product), substance use prior to or during sex, as evidenced by participant responses to interviewer-administered questionnaires and focus group.
- Proportion of scheduled HIV testing appointments that are missed, in relation to individual characteristics (age, sex, number of partners, use of other prevention methods) and the characteristics of the product.

Consistent with the exploratory objective to assess the HIV incidence in study participants during the course of study participation, the following endpoint will be assessed:

- HIV infection, as measured by seroconversion of study participants during the approximate 12 months of follow-up

Exploratory Endpoints:

- Consistent with the exploratory study objective to explore the feasibility of biofeedback of Blood Spot results as an adherence enhancing strategy in 150 HIV-negative adolescents, ages 15-19 years, the following exploratory endpoints will be assessed:

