10.6 DATA ANALYSIS PLAN

A customized data entry and management system will be implemented for the project in Microsoft Access. Data will be analysed using the statistical programme STATA (Stata Corporation, College Station, Texas, USA). Simple descriptive statistics including frequency distributions will be used to assist in data cleaning and summarization.

The analysis plan for each of the study objectives (per 10.2 above) is detailed below. (Note that throughout the analysis, all statistical tests will be 2-sided using an alpha of 0.05.)

Endpoints:

A. PRIMARY

1. Primary: Use

Number of adolescents who continue to use PrEP after the initial 3 month period and the total time on PrEP for each adolescent and for the cohort as a whole.

Analysis:

Proportions of participants (a) willing to use and (b) taking up PrEP will be described with point estimates and exact 95% confidence intervals. “Remaining on PrEP” will be defined as any self-reported use of PrEP at each study interval (regardless of adherence) over the 9-month follow-up period, as a binary outcome. The first 3-month “use” will be 100% for all 150 participants. We will use product-limit methods to examine ‘survival’ proportions for participants remaining on PrEP, accounting for censoring due to loss to follow-up. We will (i) examine the reasons for discontinuation

and (ii) examine the baseline and/or pre-LTF characteristics of those LTF, and compare to those retained, in order to understand the possible associations between LTF and adherence and/or sexual risk taking. While our preliminary analyses will presume this censoring is uninformative, we will include analyses that assume LTF are non-adherent. Our intention is to (i) examine the reasons for discontinuation and (ii) examine the baseline and/or pre-LTF characteristics of those LTF, and compare to those retained, in order to understand the possible associations between LTF and adherence and/or sexual risk taking. While our preliminary analyses will presume this censoring is uninformative, we will include analyses that assume LTF are non-adherent. In subsidiary analyses for this primary endpoint, we will also examine the factors associated with PrEP willingness, uptake and “remaining on PrEP” using standard methods (including chi-square and exact tests for the comparisons of proportions, and log-rank tests for the comparison of ‘survival’ curves in product-limit analysis).

2. Primary: Acceptability

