CHAMPS: Choices For Adolescent Prevention Methods for SOUTH AFRICA

Pilot study B: “PlusPills”

A Demonstration Open Label Study to Assess the Acceptability and Use of Truvada Pre-exposure Prophylaxis in Healthy, HIV-Uninfected Adolescents, 15-19 Years of Age.

STATISTICAL ANALYSIS PLAN

OVERVIEW AND SUMMARY OF DESIGN

The study is designed as an open-label phase 2 demonstration project, to evaluate the acceptability, safety, feasibility, as well as the adherence to daily oral PrEP (FTC/TDF) for HIV-1 prevention, among 150 male and female adolescent participants at two sites (with approximately 75 participants at each site), ranging in ages between 15 and 19 years old, over a 12 month period. The study will also investigate the uptake and utility of feedback to the participants real time about drug levels obtained from dried blood spots/plasma during adherence counselling.

STUDY ENDPOINTS

Primary Acceptability/Use Endpoints:

Consistent with the primary study objective to evaluate the acceptability and use of daily oral PrEP (FTC/TDF) in HIV-negative adolescents, ages 15-19 years, the following primary safety endpoints will be assessed:

- The proportion of participants who report willingness to use the study regimen, take up PrEP and remain on PrEP as part of a comprehensive prevention package.
- An acceptability questionnaire will be administered at the final study visit to assess the delivery of PrEP and the content of the study visits, including the user-friendliness of the medication regimen (including an assessment of side effects), the delivery format, the dosing strategy, and the clinic visit schedule.
- Number of adolescents recruited, enrolled, and retained in the study.

Primary Safety Endpoint:

CHAMPS: Choices For Adolescent Prevention Methods for SOUTH AFRICA

Pilot study B: “PlusPills”

A Demonstration Open Label Study to Assess the Acceptability and Use of Truvada Pre-exposure Prophylaxis in Healthy, HIV-Uninfected Adolescents, 15-19 Years of Age.

- Grades 2, 3, and 4 clinical and laboratory adverse events;

Secondary Endpoints:

Consistent with the secondary study objectives to evaluate the adherence and sexual behaviour of daily oral PrEP (FTC/TDF) in HIV-negative adolescents, ages 15-19 years, the following endpoint will be assessed:

Adherence Endpoint:

- Adherence to daily regimens of oral PrEP as evidenced by self-report, pill counts, and proportion of participants assigned to FTC/TDF who have detectable drug levels.

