participants. Should the SMC or the PSRT detect evidence of harm such that the recommendation for halting or modifying the study is made, then this will be communicated to the PI, The protocol team and the DAIDS prevention division. The IRB and MCC will also be informed of the discontinuation of the study and/or the modification and reasons for modification of the study. All further enrollment, and study activities other than safety follow up will be put on hold. Participants, guardians and CABS will be notified as soon as possible after next steps are identified.

DATA ANALYSIS PLAN

A customized data entry and management system will be implemented for the project in Microsoft Access. Data will be analysed using the statistical programme STATA (Stata Corporation, College Station, Texas, USA). Simple descriptive statistics including frequency distributions will be used to assist in data cleaning and summarization.

The analysis plan for each of the study objectives (per 10.2 above) is detailed below. (Note that throughout the analysis, all statistical tests will be 2-sided using an alpha of 0.05.)

Endpoints:

A. PRIMARY

1. Primary: Use

Number of adolescents who continue to use PrEP after the initial 3 month period and the total time on PrEP for each adolescent and for the cohort as a whole.

Analysis:

Proportions of participants (a) willing to use and (b) taking up PrEP will be described with point estimates and exact 95% confidence intervals. “Remaining on PrEP” will be defined as any self-reported use of PrEP at each study interval (regardless of adherence) over the 9-month follow-up period, as a binary outcome. The first 3-month “use” will be 100% for all 150 participants. We will use product-limit methods to examine ‘survival’ proportions for

CHAMPS: Choices For Adolescent Prevention Methods for SOUTH AFRICA

Pilot study B: “PlusPills”

A Demonstration Open Label Study to Assess the Acceptability and Use of Truvada Pre-exposure Prophylaxis in Healthy, HIV-Uninfected Adolescents, 15-19 Years of Age.

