A Demonstration Open Label Study to Assess the Acceptability and Use of Truvada Pre-exposure Prophylaxis in Healthy, HIV-Uninfected Adolescents, 15-19 Years of Age.

sum tests, replaced by analysis of variance or u-tests for global comparisons across polytomous groupings.

3. Primary: Safety

Grades 2, 3, and 4 clinical and laboratory adverse events

Analysis:

This analysis will be based on descriptive statistics.

B. Secondary Endpoints:

1. Secondary: Adherence

Adherence to daily regimens of oral PrEP as evidenced by the use self-report, pill counts, and proportion of participants on FTC/TDF who have detectable drug levels.

Proportion of doses that are taken as instructed.

Proportion of blood samples with detectable drug levels

Proportion of adolescents with detectable drug levels who report using PrEP

Analysis Plan:

There are 3 different measures of PrEP adherence that will be used for the primary adherence endpoint: Participant self-report, pill count results, and detectable drug levels.

While the distributions of each of these measures may vary, a priori we anticipate that analysis of each of these 3 measures will use two different binary metrics from data at each study visit: (i) perfect adherence (defined as adherence data that do not suggest any missed doses, e.g., pill count data consistent with daily dosing, or no missed doses detected on self-report); and, (ii) effective adherence (defined as adherence levels that are consistent with protection against HIV exposure based on available data from PrEP efficacy trials, e.g., >85% doses taken, from pill count, or self-report; or therapeutic drug levels on biological assays).

Note that drug levels will be used in analyses of effective adherence only.

Analyses of adherence data will be based on the binary constructs of perfect and effective adherence as well as continuous measures of the proportion of PrEP doses taken; both the

CHAMPS: Choices For Adolescent Prevention Methods for SOUTH AFRICA

Pilot study B: “PlusPills”

A Demonstration Open Label Study to Assess the Acceptability and Use of Truvada Pre-exposure Prophylaxis in Healthy, HIV-Uninfected Adolescents, 15-19 Years of Age.

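### Primary Use is measured by drug level in protocol 4.2 but by self-report in protocol 10.6 and SAP A.1, and no planned Use analysis delivers the 4.2 endpoint

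*SAP*

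**What the plan says.** Six places in the two documents bear on the primary Use endpoint.

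- Protocol 4.2 gives the first Use endpoint as "Number of adolescents who continue to use PrEP (as indicated by DBS/ plasma levels) after the initial 3 month period". The second is "The total time on PrEP for each adolescent (as indicated by DBS/plasma levels) and for the cohort as a whole in those individuals" who indicated use by self-report when each 3-month period began. The drug-level parenthesis clearly attaches to the individual's time. For the cohort total the wording is ambiguous.
- The Protocol Summary names no measure for the number continuing. Its second Use endpoint is "The total time on PrEP for each adolescent and for the cohort as a whole by self report".
- Protocol 10.6, under Primary: Use, restates both endpoints without a measure. It then defines remaining on PrEP as any "self-reported use of PrEP at each study interval (regardless of adherence"), analysed by product-limit methods.
- SAP A.1 repeats that text: remaining on PrEP "will be defined as any self-reported use of PrEP at each study interval (regardless of adherence) over the 9-month follow-up period".
- Protocol 10.2 and the SAP endpoint list refer to participants who "take up PrEP and remain on PrEP as part of a comprehensive prevention package", to the acceptability questionnaire, and to the "Number of adolescents recruited, enrolled, and retained in the study". They attach no measure to remaining on PrEP and do not list total time.

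Drug levels enter the SAP under B.1, secondary adherence. The outputs there include the proportion of participants on FTC/TDF with detectable levels, the proportion of samples with detectable levels, and the "Proportion of adolescents with detectable drug levels who report using PrEP". The B.1 analysis text (also in 10.6) adds that drug levels serve the effective-adherence analyses only.

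**The concern.** A primary endpoint has two different measures in current text, and only one has an analysis. Followed as written, the plan cannot report the drug-level endpoint that 4.2 makes primary.

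The choice of measure matters in this trial. Protocol 2.5 recounts that participants in earlier PrEP trials reported pill use that drug levels did not bear out, and it hopes this design will give a truer picture of usage. Section 2.6.7 says that self-report overstated adherence in several trials. A reader of 4.2 would expect the headline Use result to be drug-confirmed. A reader of 10.6 or the SAP would expect it to be self-reported.

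**Working it through.** **1. The passages side by side**

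| Place | Number continuing / remaining on PrEP | Total time on PrEP |
|---|---|---|
| Protocol Summary | no measure named | self-report |
| Protocol 4.2 | DBS/plasma level | DBS/plasma level per adolescent; cohort wording ambiguous |
| Protocol 10.2 | no measure named | not listed |
| Protocol 10.6, A.1 | any self-report | restated, no measure |
| SAP endpoint list | no measure named | not listed |
| SAP A.1 | any self-report | restated, no measure |

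The rest of the A.1 text covers willingness, uptake, loss to follow-up, reasons for stopping and associated factors. It never uses a drug level.

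**2. What the planned outputs can supply**

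B.1 analyses adherence at each visit and lists proportions with detectable drug. From these, a by-visit count of drug-confirmed users could largely be derived. It would still be a secondary adherence result, and the effective-adherence metric refers to therapeutic levels while the listed proportions refer to detectable ones. Nothing planned turns drug levels into time on PrEP. After week 12 the samples fall at weeks 24, 36 and 48, so one sample would stand for 12 × 7 = 84 days. The plan has no rule for crediting that interval.

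**3. The plan's own figures**

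- Enrolment: 135 / (1 − 0.10) = 150, as stated.
- Exact 95% limits for 14/135: 5.79% to 16.79%, against the stated 5.7 and 16.8 in the 10% row.

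Both figures reproduce, and neither depends on how Use is measured.

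**4. Illustration of size**

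The documents give no drug-detection rate among self-reported users, so this rests on three assumptions:

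- f = self-reported non-use, set at 0.10. The figure is borrowed from the sample-size section, where 10% is the frequency of a non-acceptability endpoint and is not described as self-reported.
- d = probability of detectable drug given self-reported use, set at 1.00, 0.90 or 0.70.
- No detection in participants who report non-use.

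Drug-level non-use = 1 − (1 − f) × d. At n = 135, self-reported users = 135 × 0.90 = 121.5.

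| d | Drug-level non-use | Drug-confirmed users | Gap |
|---|---|---|---|
| 1.00 | 1 − 0.90 = 10% | 121.5 | 0 |
| 0.90 | 1 − 0.81 = 19% | 121.5 × 0.90 = 109.35 | 12.15 |
| 0.70 | 1 − 0.63 = 37% | 121.5 × 0.70 = 85.05 | 36.45 |

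The definitions agree if every reporter has detectable drug. At d = 0.90 the estimate passes the 16.8% upper limit of the planning row. At d = 0.70 it leaves the 5% to 20% planning range. Any detection in non-reporters would lower drug-level non-use.

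**5. Who is sampled after stopping**

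- Protocol 7.4 lists drug levels at weeks 12, 24, 36 and 48 without restriction.
- Protocol 7.8 restricts weeks 36 and 48 to those remaining on product, but not week 24.
- Protocol 7.6 drops drug levels for participants who choose to stop. For those stopped by the investigator or withdrawing permanently it applies the week-48 procedures, which include drug levels under 7.4.
- Table 1 marks weeks 24 to 52 as on PrEP only.

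These passages differ, so the documents do not settle which stoppers would have a sample.

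**The case against.** The strongest reply is that the plan has already chosen. Protocol 10.6 and SAP A.1 carry the same operational rule under the heading Primary: Use. The Summary gives total time by self-report. Protocol 2.5 assesses adherence among those who self-report use, which makes self-report the way users are identified. The B.1 note limits drug levels to effective adherence. Against all this, 4.2 has two parentheses in a section that summarises endpoints. Most of this stands: self-report is the operative measure. It does not remove the conflict, because 4.2 is current text, the SAP never mentions or withdraws it, and the B.1 note appears in a passage about adherence metrics.

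A reader might infer three stronger things that the documents do not support.

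- That the sponsor is free to call either result primary once the data are seen. The analysis text points one way, so this overstates the latitude.
- That self-report is the wrong measure. Section 2.6.7 treats persistent use and quality of adherence as separate aspects, so measuring persistence by self-report is defensible. The design also tries to remove the incentive to over-report by not making participation after the first 3 months depend on pill use.
- That some 12 or 36 participants would be misclassified. Those figures come from assumed detection rates with no source in the documents.

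It is also fair to say that Use is reported mainly by proportions, confidence intervals and survival curves in a single-arm study. The consequence is unclear reporting of a primary endpoint, not a faulty treatment comparison.

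**Conclusion.** The inconsistency is real and is established by the text alone. Protocol 4.2 defines primary Use by drug level, the analysis sections define it by self-report, and no Use analysis yields the 4.2 version. Drug-confirmed time on PrEP is the clearest gap, since it cannot be obtained from the planned adherence outputs. The numerical consequence is unknown: zero if all reporters have detectable drug, and 9 or 27 percentage points of non-use (19 − 10; 37 − 10) under the assumed 90% or 70% detection. This should be fixed, but it does not invalidate the design, because the operative measure can be inferred and the remedy is mainly alignment plus one supportive analysis.

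**What to change.** Required: state one primary Use definition in identical words in the Summary, 4.2, 10.2, 10.6, the SAP endpoint list and SAP A.1. Prespecify the other as a supportive Use analysis reported beside it, and amend the effective-adherence-only note in 10.6 and SAP B.1 to allow it. The smallest edit keeps self-report as primary and adds drug-confirmed continuation and drug-confirmed time as supportive. Making drug level primary is also defensible.

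For the drug-level version:

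- Name the assay matrix and its detection limit; 4.2 allows either DBS or plasma.
- Report attenders with no sample result as a separate category, with sensitivity analyses counting them first as users and then as non-users. Leave those lost to follow-up to the analyses already planned in A.1.
- State that one sample per 12-week interval can over-credit or under-credit that interval. Protocol 2.5 links the non-cellular assay used for real-time feedback to recent drug levels.
- Reconcile 7.4, 7.6, 7.8 and Table 1 on who is sampled after stopping.

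The cost is a protocol and SAP amendment and some extra analysis. On-PrEP samples are already scheduled at weeks 24, 36 and 48, so no visits or samples are added. The price of adding none is that drug-confirmed time stays coarse.

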participants remaining on PrEP, accounting for censoring due to loss to follow-up. We will (i) examine the reasons for discontinuation and (ii) examine the baseline and/or pre-LTF characteristics of those LTF, and compare to those retained, in order to understand the possible associations between LTF and adherence and/or sexual risk taking. While our preliminary analyses will presume this censoring is uninformative, we will include analyses that assume LTF are non-adherent. Our intention is to (i) examine the reasons for discontinuation and (ii) examine the baseline and/or pre-LTF characteristics of those LTF, and compare to those retained, in order to understand the possible associations between LTF and adherence and/or sexual risk taking. While our preliminary analyses will presume this censoring is uninformative, we will include analyses that assume LTF are non-adherent. In subsidiary analyses for this primary endpoint, we will also examine the factors associated with PrEP willingness, uptake and “remaining on PrEP” using standard methods (including chi-square and exact tests for the comparisons of proportions, and log-rank tests for the comparison of ‘survival’ curves in product-limit analysis).

2. Primary: Acceptability

An acceptability questionnaire will be administered 3 monthly to assess reasons for continuing, stopping or restarting PrEP. A further questionnaire will be administered at the final study visit to assess the delivery of PrEP and the content of the study visits, including the user-friendliness of the medication regimen (including an assessment of side effects), the delivery format, the dosing strategy, and the clinic visit schedule.

Analysis Plan:

This acceptability questionnaire will contain both binary items as well as continuous (interval) measures from Likert-type items. Analysis of data from this questionnaire will begin with standard descriptive statistics for each item, overall and by key participant subgroups (a priori, these will be based on participant age, gender, sexual activity during the study and PrEP adherence during the study). We will compare responses to acceptability items using standard methods, including chi-square and exact tests; Student’s t- and rank-

CHAMPS: Choices For Adolescent Prevention Methods for SOUTH AFRICA

Pilot study B: “PlusPills”

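### The primary Use endpoint rests on two conflicting data sources, and total time on PrEP has no stated computation

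*SAP*

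**What the plan says.** The Protocol Summary lists as a primary Use endpoint "The total time on PrEP for each adolescent and for the cohort as a whole by self report". Protocol 4.2 lists the same endpoint as "The total time on PrEP for each adolescent (as indicated by DBS/plasma levels) and for the cohort as a whole", restricted to those who reported use at the start of each 3-month period. It also lists "Number of adolescents who continue to use PrEP (as indicated by DBS/ plasma levels) after the initial 3 month period".

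The SAP (Data Analysis Plan, A.1 Primary: Use, repeated in Protocol 10.6) names the number continuing and the total time. It defines remaining on PrEP as "any self-reported use of PrEP at each study interval (regardless of adherence"), a binary outcome over the 9 months after the initial period. The method is "We will use product-limit methods to examine" survival proportions for "participants remaining on PrEP, accounting for censoring due to loss to follow-up". The same paragraph says that use in the first 3 months "will be 100% for all 150 participants".

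Stopping and restarting are part of the design (Protocol Summary, Design; 4.1; 4.3; 7.4). Participants may opt out at any time (4.1, 4.3), and product is stopped for HIV infection or pregnancy (7.10.1, 7.10.2).

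**The concern.** The two protocol definitions of total time use different data and need not agree. The number continuing has the same problem: Protocol 4.2 requires drug levels, while the SAP's definition of remaining on PrEP rests on self-report. For total time the SAP gives no source, unit, rule for assigning intervals or summary statistic, so it does not settle the matter.

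The protocol gives its own reason to expect that the choice matters. Section 2.5 says that women in two earlier PrEP trials reported high use while their drug levels showed very poor use, and 2.6.7 describes over-reporting of adherence in several trials. If the source is chosen after the data are seen, a primary result is open to selection.

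Two smaller matters sit in the same paragraph. First 3-month use is stipulated, although the protocol's own rules allow it to fall below 100%. And the product-limit analysis does not name its event in a design where people can restart.

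**Working it through.** **The plan's own figure.** 135 / (1 − 0.10) = 150, as stated. The exact 95% limits for 14 of 135 are 5.8% and 16.8%, against the printed 5.7 and 16.8. The sizing is not at issue here.

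**The sources side by side.**

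| Place | Number continuing | Total time |
|---|---|---|
| Protocol Summary, Primary endpoints | no source stated | self-report |
| Protocol 4.2 | drug levels | drug levels, among those reporting use at the start of each period |
| SAP A.1 and Protocol 10.6 | remaining on PrEP, by self-report | named; no source or computation |
| SAP Study Endpoints and Protocol 10.2 | proportion willing, taking up and remaining; no source stated | not listed |

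Rows 1 and 2 contradict each other on total time. Rows 2 and 3 contradict each other on continued use.

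**What the source could do (illustration; every rate is assumed).** Decisions fall at weeks 12, 24 and 36 (Protocol 7.4). Assume no losses, 10% ever stopping, and 20% of those off PrEP restarting at each later decision.
- Stop probability per decision: s = 1 − 0.90^(1/3) = 0.0345.
- Share on PrEP: on_k = on_(k−1) × (1 − s) + (1 − on_(k−1)) × 0.2, starting from 1. This gives 0.965, 0.939 and 0.919.
- Mean self-reported time, weeks 12 to 48: 12 × (0.965 + 0.939 + 0.919) = 33.9 weeks.
- Let d be the share of reported intervals with detectable drug. Drug-level time is d × 33.9: 33.9 weeks if d = 1, 30.5 if d = 0.9, 16.9 if d = 0.5.

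This treats each 12-week interval as wholly detectable or not. Protocol 4.2 states no rule for turning a visit's drug level into time.

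**Restarts.** With first stop as the event, the curve at the last interval is (1 − s)^3; the share on PrEP follows the recursion above.

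| s per decision | restart per decision | first-stop curve | on PrEP |
|---|---|---|---|
| 0.0345 | 0.2 | 90.0% | 91.9% |
| 0.1 | 0.2 | 72.9% | 78.1% |
| 0.3 | 0.5 | 34.3% | 62.8% |

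The gap runs from 1.9 to 28.5 points here and is zero if nobody restarts. It depends wholly on the assumed rates.

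**The 100% sentence.** Full use credits 150 × 12 = 1,800 person-weeks. If use fell in a straight line to a share u at week 12 (assumed), the overcount would be 150 × 12 × (1 − u) / 2: 45 person-weeks at u = 0.95 and 270 at u = 0.70. This arises only if the 100% is carried into a total.

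**The case against.** The strongest reply is that most of the machinery exists. The per-interval binary outcome already classes a restarter as on PrEP, and continuing users can be counted from it. A reader might infer that the product-limit analysis is invalid without a restart rule. The documents do not support that: time to first discontinuation is a sound measure of persistence, which Protocol 2.6.7 names as one of three aspects of adherence under study. What remains is a label. Loss to follow-up is also covered, by censoring and by an analysis that treats those lost as non-adherent.

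A reader might infer that the 100% sentence biases the results. No section carries the figure into a use or time total. It may be only a starting convention for a curve that begins at month 3, and early adherence is still analysed at each visit as a secondary endpoint. The sentence still states as fact something the protocol plans to ascertain (4.1).

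A reader might take "Note that drug levels will be used in analyses of effective adherence only" as barring drug levels from the Use endpoint. It does not. It stands in the Secondary: Adherence analysis and separates effective from perfect adherence; it sets no source for Use.

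A reader might treat the 5% to 20% frequencies in the sample size table as stopping rates over follow-up. The documents describe them as frequencies of non-uptake and use, so they cannot anchor the size of a restart gap.

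Finally, Protocol 2.5 argues that separating participation from pill-taking after month 3 should make reported use more accurate. That may narrow the gap between self-report and drug levels, but it does not say which of them defines the endpoint.

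**Conclusion.** The source conflict stands and should be resolved before analysis: the Protocol Summary and Protocol 4.2 cannot both be followed for total time, Protocol 4.2 and the SAP disagree on continued use, and the computation of total time is missing. This rests on the text alone.

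The size of the effect is unknown. The figures above show only that the two sources agree if every reported interval has detectable drug and separate in proportion as fewer do.

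The 100% sentence should be replaced because opt-out, HIV infection or pregnancy before week 12 could make it false. It would overstate early use only if someone stops or reports no use and the figure is carried forward. The restart point is minor wording.

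**What to change.** 1. Reconcile the Protocol Summary, Protocol 4.2, Protocol 10.6 and SAP A.1 to one pre-specified source for both the number continuing and total time. Self-report matches the Summary and the SAP's definition of remaining on PrEP. Report the version confirmed by drug level as a sensitivity analysis, with a stated rule for classing an interval.
2. Define each person's total time as the sum of all intervals on PrEP, including those after a restart, then sum over the cohort. State that whole-interval counting credits the full interval to someone who stops partway.
3. Replace the 100% sentence in SAP A.1 and Protocol 10.6 with observed use at weeks 4, 8 and 12.
4. Minor wording: label the product-limit and log-rank analyses as time to first discontinuation. Report the existing per-interval outcome as the proportion on PrEP with exact 95% confidence intervals, counting restarters as on PrEP.

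The cost is wording in the SAP and the protocol and a few tables. The schedule table already has adherence assessments at weeks 4, 8, 12, 24, 36 and 48, and drug levels at the same visits (from week 24, for those on PrEP). Sample size and visits do not change.
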